### 3.2.3 EXCLUSION CRITERIA DURING SURGERY

1. Vitreous loss prior to use of the investigational device
2. Positive posterior pressure preventing safe implantation of the lens system
3. Anterior chamber hyphema preventing visualization of implantation
4. Any zonular or capsular rupture or capsular bag instability
5. Intraoperative miosis preventing visualization of fixation features
6. Need for concomitant procedures (e.g. glaucoma surgery, LRI, RK, LASIK, etc.)
7. Subject who, in the clinical judgment of the investigator, is not suitable for participation in the study for another clinical reason, as documented by the investigator

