**Sulcus placement of a "piggyback" IOL** is a procedure that has not been evaluated for safety and effectiveness by the FDA so the use of approved IOLs for this purpose in the U.S. is off-label. Among the complications reported with this procedure are secondary pigment dispersion, iris/pupil irregularities, chronic iritis, hyphema, glaucoma, zonular disruption and/or posterior capsular rupture. Thus, it would be desirable to be able to correct or modify the optical result without the need to implant a "piggyback" IOL with its inherent serious risks.

**IOL Exchange/Manipulation** in general, is technically challenging for the surgeon and poses an iatrogenic risk to intraocular structures including the lens capsule, iris, and endothelium of the cornea. The capsular bag fibroses weeks after IOL implantation creating a strong adhesion between the capsule and the IOL. Manipulation of the capsular bag to remove an IOL is the major risk in this setting and can damage the capsular bag including posterior capsular rupture and capsular bag dislocation. The capsular bag cannot be repaired once damaged. This risk increases over time as the capsular bag adheres to the IOL and haptics. Even when IOL exchange is not required, manipulation of traditional IOL's to rotate or center the optic introduces the risk of capsular or zonular damage which can cause further lens instability and lens malposition. Thus, it would be desirable to be able to correct RRE without the need to remove the entire IOL particularly after capsular contraction or fibrosis.

The modular IOL concept will serve as a valuable addition to the armamentarium of cataract surgeons. The goal of this technology is to improve refractive (spheric and toric) outcomes and avoid the significant risks of secondary procedures currently being performed as standard practice to address RRE in an indirect manner. It is anticipated that this modular lens will provide clinical utility in two basic areas, the first being the focus of this study.

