### 8.2.3 PER PROTOCOL POPULATION

The **Per Protocol (PP)** Population contains eyes with successful HMTIOL or HMIOL implantations during surgeries and do not have major protocol deviation (such as improperly enrolled in the study or lens power calculation errors) and will be considered the primary population for effectiveness outcomes. The effectiveness outcomes (UCDVA, BCDVA, and prediction error) will be evaluated based on the per protocol population.

The protocol deviations will be determined reviewed by ClarVista clinical personnel prior to analysis.

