5.9.6. REDUCTION IN CYLINDER POWER

Reduction in cylinder power will be calculated for each eye implanted with the HMTIOL as follows:

Cylinder Power Reduction = absolute value of preoperative magnitude of corneal cylinder (K) – absolute postoperative magnitude of MRCYL at the corneal plane.

The percent reduction in cylindrical power will be calculated for eyes with non-zero preoperative corneal cylinder as follows:

Cylinder Power % Reduction = Cylinder Power Reduction/ absolute value of preoperative magnitude of corneal cylinder (K) $\times 100$.

Descriptive statistics for continuous variables will be used to summarize these outcomes at each visit.

6. Sample Size

Based on a one-sided two-sample non-inferiority t-test with a significance level of 0.05, a sample size of 25 bilateral subjects (50 total eyes, 25 in each cohort) with successful implants and 3-month follow-up ECC data for each eye provides a power of 80% to reject the null hypothesis if the true difference in mean ECC percent change is 5%, the standard deviation of the ECC percent change is 12.6%.

It should be noted that some study subjects may not have successful implants in both eyes due to intraoperative eligibility, or do not have the 3-month ECC data for both eyes. These subjects will be excluded from the ECC comparisons. With an assumption of a dropout rate of approximately 20%, a sample size of 32 bilateral subjects should be enrolled.

7. Analysis Populations

Subjects that are screened but disqualified based on the preoperative and intra-operative eligibility criteria will be excluded from the safety and performance data analyses. However, their reasons for the screen failure will be summarized. The analyses populations are defined below.

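### Item 4 of protocol 3.2.3 (also item 7, arguably item 5) has no before-device limit, so under protocol 8.2 and SAP 7 an optic-exchange complication can remove a subject whom the Safety Population rule keeps

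*Protocol*

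**What the plan says.** Protocol 3.2.3 has seven criteria for exclusion during surgery, and they differ in reach.

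- Item 1 has an explicit limit: "Vitreous loss prior to use of the investigational device".
- Items 2 and 3 are tied by their own words to implantation: "Positive posterior pressure preventing safe implantation of the lens system" and "Anterior chamber hyphema preventing visualization of implantation".
- Item 4 has no limit of time or cause: "Any zonular or capsular rupture or capsular bag instability".
- Item 5 has no time limit: "Intraoperative miosis preventing visualization of fixation features".
- Item 6 covers the need for concomitant procedures, with glaucoma and refractive surgery as examples.
- Item 7 is open-ended investigator judgement.

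Protocol 8.2 and SAP 7 exclude subjects disqualified on preoperative or intraoperative eligibility from the safety and effectiveness (SAP: performance) analyses and report them as screen failures. SAP 6 expects losses from the ECC comparison because "some study subjects may not have successful implants in both eyes due to intraoperative eligibility".

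Other text keeps such eyes. The synopsis, protocol 8.2.1 and SAP 7.1.1 put every eye with attempted study-lens implantation in the safety analysis; the two population definitions include attempts aborted after contact. Protocol 6.2 lists a capsular tear during surgery to implant the study device as an example of an adverse event.

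**The concern.** The optic exchange is the procedure under test in Cohort 2, and protocol 2.0 makes endothelial cell loss after it a specific objective. Cohort 1 surgery has no exchange step. A rupture during the exchange meets item 4 as written, so complications of the tested procedure can become eligibility failures in the one cohort that has that procedure.

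Protocol 8.2 and SAP 7 speak of subjects, not eyes, so the fellow eye would go too. In an odd-numbered subject, whose Cohort 1 eye is operated on first (3.3.2), that eye normally already carries a study lens.

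Two results are exposed: the Cohort 2 complication rate and the paired ECC comparison. Losing a few subjects matters little for precision. What matters is that the loss would depend on the outcome and fall on the eyes with the worst exchanges.

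**Working it through.** **1. The plan's own figure.** SAP 6 inflates 25 evaluable bilateral subjects for about 20% loss, a loss that includes intraoperative ineligibility: 25 / (1 − 0.20) = 31.25, rounded up to 32. This reproduces. Up to 32 Cohort 2 eyes are therefore at risk of an exchange complication.

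**2. Which rule applies to an eye whose capsule ruptures during the exchange and which keeps its lens?**

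| Text | Result for that eye |
|---|---|
| Protocol 3.2.3 item 4 | Meets the exclusion criterion |
| Protocol 8.2, SAP 7 | Subject leaves the safety and effectiveness/performance analyses |
| Synopsis, protocol 8.2.1, SAP 7.1.1 | Eye stays in the safety analysis |
| Protocol 6.2 | Closest listed example, a capsular tear while implanting the device, is an adverse event |
| Protocol 8.2.2, SAP 7.1.2 | Eye fits the Implanted-Eye Population, so the pair stays in the ECC comparison if 3-month data exist for both eyes |
| Protocol 4.9 with 8.2.3 | Per Protocol status undefined |

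SAP 2 makes the SAP supersede the protocol, but the SAP contains both rules (7 and 7.1.1), so precedence does not settle the matter. For ECC, the route out for an eye that keeps its lens is the sentence in protocol 8.2 and SAP 7. The ECC comparison is not run on the Per Protocol set.

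**3. Illustration for the complication rate.** The event counts k are assumed, because the documents give no exchange complication rate. Assume also that all 32 Cohort 2 eyes are otherwise in the safety analysis and that no other such event occurs. The one-sided 95% upper limit U is exact binomial: P(X ≤ k | n, U) = 0.05. For k = 0 this reduces to U = 1 − 0.05^(1/n).

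| Assumed k | Events kept | Subjects excluded |
|---|---|---|
| 1 | 1/32 = 3.1%, U = 14.0% | 0/31, U = 9.2% |
| 2 | 2/32 = 6.3%, U = 18.4% | 0/30, U = 9.5% |
| 3 | 3/32 = 9.4%, U = 22.5% | 0/29, U = 9.8% |

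SAP 5.5 compares a one-sided *lower* 95% limit with the ISO rate. For k = 2 that limit is 1.1% if the events are kept and 0 if they are excluded.

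**4. Chance that the question arises.** P(at least one event in 32 eyes) = 1 − (1 − p)^32. For assumed rates p of 2%, 5% and 10% this is 48%, 81% and 97%.

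**5. Power.** The readable text gives no non-inferiority margin, so the stated 80% cannot be verified. Take the distance between margin and true difference that would give 80% in a two-sample t-test with 25 eyes per cohort and SD 12.6, about 9.0 points. Losing two subjects on top of 20% dropout leaves (32 − 2) × 0.8 = 24 pairs, and power falls to about 78.5%. The harm is selective removal, not lost power.

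**The case against.** The best reply is that the intraoperative criteria are gates to implantation. Protocol 8.2 and SAP 7 speak of screened subjects and screen failures. SAP 6 ties intraoperative eligibility to eyes without a successful implant. Protocol 3.3.2 lets the surgeon keep the existing optic when it cannot be exchanged and does not call that an exclusion. Protocol 4.5 limits its complication-based discontinuation rule to complications unrelated to the device that prevent implantation in both eyes. This may well be what the authors meant. But item 4 does not say so, although item 1 and section 4.5 show that such limits were written where wanted.

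Four stronger readings are tempting, and the documents do not support them.

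- *All of items 2 to 7 are open.* Items 2 and 3 concern conditions that prevent implantation or its visualization, and item 6's examples are not exchange complications. Item 5 is arguable.
- *The protocol names capsular damage as the major risk of this exchange.* The sentence "Manipulation of the capsular bag to remove an IOL is the major risk in this setting and can damage the capsular bag" follows a description of the bag fibrosing weeks after implantation. It concerns conventional lenses, not a modular optic exchanged in the same operation.
- *The Per Protocol rule biases ECC.* That rule requires that eyes "do not have major protocol deviation (such as improperly enrolled in the study or lens power calculation errors") and covers visual acuity and prediction error. ECC uses Implanted-Eye pairs. Protocol 3.3.1 also treats a subject as enrolled once the screening criteria are met, so a later complication is not obviously improper enrolment. Section 4.9 does name eligibility as an example of a major deviation, so the point is open, not settled.
- *ECC bias of 0.5 to 4.5 points.* This comes from multiplying an assumed complication rate of 5–15% by an assumed extra loss of 10–30 points. Neither input is in the documents, and the product assumes that every affected eye is removed.

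**Conclusion.** The concern holds in a limited form. Item 4 and item 7, and arguably item 5, can be met by a complication of the optic exchange. Followed literally, protocol 8.2 and SAP 7 then remove that subject from the safety analysis and the ECC comparison. The synopsis, protocol 8.2.1 and SAP 7.1.1 say the eye stays in the safety analysis, and 6.2 treats a similar event as an adverse event. The passages conflict, so removal is possible but not established. If the conflict stands, the choice could be made after the outcomes are known.

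The size of any bias cannot be derived from the documents. The two-event example (6.3% against 0/30) shows only that, in a study of 32 subjects, one or two reclassified eyes can decide whether exchange complications are reported as zero. It rests on an assumed count and on removal of every affected subject.

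**What to change.** Reconcile the passages for analysis classification only:

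- State in protocol 3.2.3, protocol 8.2 and SAP 7 that, for the analysis sets, an intraoperative criterion disqualifies a subject only if it was met before the study lens contacted the eye. The copy of the list in the synopsis should match.
- State that a later event is recorded as an adverse event and is not by itself an eligibility failure or a major eligibility deviation. The eye and its fellow eye stay in the Safety, Implanted-Eye, ECC-pair and Per Protocol sets for which they otherwise qualify.

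An eye without a successful implant still leaves the Implanted-Eye set under the existing definition. The surgical criteria, and the surgeon's decision whether to proceed, do not change.

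The cost is a sentence or two in each place, with no added subjects, visits or measurements. The downside is that the reported Cohort 2 complication rate and ECC loss may be slightly less favourable.

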### 3.3 STUDY VISITS

The timing and frequency of each assessment to be performed at each visit, will be carried out according to "Appendix A – Schedule of Assessments."

Procedures to be followed in order to carry out each individual assessment, are under separate cover (See study specific Manual of Procedures).

In all instances, if the first study eye and secondary eye post-operative assessments cannot be seen on the same day and both remain "in-window," the subject must return for a separate visit in order to maintain "in-window" status for both eyes throughout study participation.

### 3.3.1 PRE-OPERATIVE VISIT – SCREENING/BASELINE (DAY -90 TO DAY 0)

After providing informed consent (see Section 4.1), prospective subjects will be screened to determine whether they meet enrollment criteria. Demographic information, relevant ocular history, and current ocular medication use will be collected. If all criteria are met, the subject will be considered enrolled, IOL calculation completed to determine appropriate HMTIOL or HMIOL power, and the subject scheduled for surgery.

### 3.3.2 DAY 0 VISIT (CATARACT SURGERY AND IOL IMPLANTATION)

Record any changes in concomitant medications and medical history, prepare the subject for surgery in the study eye (see Surgical Procedure Guide), and re-review inclusion/exclusion criteria to ensure subject still qualifies to participate.

All subjects with an odd subject number will have their Cohort 1 eyes done first. All subjects with and even subject number will have their Cohort 2 eyes done first.

The Investigator will carry out the surgical procedure and HMTIOL or HMIOL implantation as specified in the Surgical Procedure Manual and the following details will be captured in both Source Documents and eCRFs:

- Date of surgery
- Operative eye
- Cohort 1 or Cohort 2
- Incision location and size
- Ophthalmic Viscoelastic Device (OVD) used
- All medication used pre-, intra-, and post-operatively (ophthalmic and systemic)
- Model, serial number, and diopter of HMTIOL or HMIOL implant components
- Toric IOL power and axis orientation (for HMTIOL)
- IOL injection device

Once the subject is confirmed stable post-surgery, provide IRB / EC approved post-operative instructions and discharge.

Record any AEs, adverse device effects (ADEs), unexpected adverse device effects (UADEs), or device deficiencies (DD) (see Sections 6.1.1, 6.1.2, 6.1.3, or 6.1.4 respectively) observed pre-, intra-, or post-operatively.

In the event the subject is not implanted with the HMTIOL or HMIOL, the surgeon will provide the best care option to the patient, including implanting a commercially available IOL. In the event the optic cannot be exchanged, the surgeon will provide the best care option to the patient, including keeping the existing optic.

In the event the subject is not implanted with an HMTIOL or HMIOL device due to an intra-operative complication, the subject will be discontinued (see Section 4.5).

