## 2.0 OBJECTIVES

The objective of this pilot study is to demonstrate the safety and efficacy of the HARMONI™ Modular Toric IOL in patients with pre-existing astigmatism.

The specific objectives are:

- To evaluate endothelial cell loss after an intraoperative optic exchange.

- To evaluate refractive outcomes, astigmatism correction with HMTIOL used in primary surgery.

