7.1.2. IMPLANTED-EYE POPULATION

The Implanted-Eye Population consists of eyes with successful HMTIOL or HMIOL implantations during surgeries. Since it is important to evaluate HMTIOL or HMIOL's effect on the study eyes, the assessment of ECC, slit lamp examination, intraocular pressure (IOP), and dilated fundus examination (DFE) will be based on the implanted-eye population. It should be noted that the ECC comparison between Cohort 1 and Cohort 2 of this study will be based on the subjects with successful implants in both eyes and have available ECC data at 3 months.

Additionally, the UCDVA, BCDVA, prediction error, and meridian rotation will be evaluated based on the implanted-eye population.

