**8. Interim Analyses**

There are no plans for formal interim analyses for the purposes of study modification or possible early termination. Any interim analyses will be administrative in nature and results will not be distributed to Investigators or subjects to prevent bias from exposure to accruing study results.

SAP CP-00002

[figure not shown]
ClarVista Medical, Inc.

9. Deviations from the Statistical Analysis Plan

Any deviations from the Statistical Analysis Plan will be noted and described with appropriate statistical and clinical rationale as needed. Discrepancies from the Investigational Plan are noted. The primary change is the use of a paired t-test instead of a two-sample t-test to test the primary hypothesis. This change more appropriately accounts for within-patient correlation in ECC. A secondary change was the use of "ECC" rather than "ECL" in Sections 6 and 7 above. ECL is defined in the protocol as follows: "a negative ECC percent change represents an ECC percent loss (ECL)." Since a comparison of 3-month to Pre-operative data may not always result in a measurable loss (e.g., due to measurement error of instrumentation combined with minimal actual ECC loss), ECC is determined to be a more appropriate term.

10. References

1. ISO 11979-7:2014 Ophthalmic implants — Intraocular lenses — Part 7: Clinical investigations.

Alcon - Business Use Only

Document: TDOC-0055985

Status: Effective

Effective Date: 24-Apr-2019

Version: 1.0; CURRENT; Most-Recent; Effective

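### A Cohort 2 eye whose optic was not exchanged can be analysed as an exchange eye in the endothelial cell comparison; a supportive completed-exchange analysis and a record of exchange status should be added

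*Protocol*

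**What the plan says.** Protocol 2.0 gives as a specific objective: "To evaluate endothelial cell loss after an intraoperative optic exchange". SAP 1 repeats it.

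The eye with the higher corneal astigmatism goes to Cohort 1 and the other to Cohort 2, where an exchange is planned (Protocol 3.1, SAP 4). Cohort is therefore fixed before surgery and does not depend on whether the exchange is done.

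Protocol 3.3.2 provides for an exchange that does not take place: "In the event the optic cannot be exchanged, the surgeon will provide the best care option to the patient, including keeping the existing optic". Non-implantation leads to discontinuation (Protocol 3.3.2, 4.5), but non-exchange does not. Protocol 4.4 joins implantation and exchange by an and/or, so a subject can complete the study without an exchange.

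SAP 7.1.2 bases the ECC comparison between cohorts on "the subjects with successful implants in both eyes and have available ECC data at 3 months". Protocol 8.2.2 has the same rule, worded as ECL. SAP 6 names two reasons for leaving the comparison, unsuccessful implantation in both eyes and missing 3-month ECC, and does not mention a failed exchange. The Per Protocol population (Protocol 8.2.3, SAP 7.1.3) is assigned to UCDVA, BCDVA and prediction error, not to ECC.

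**The concern.** The population rule and the objective do not describe the same eyes. The objective concerns an eye that has had an exchange. The rule admits any implanted Cohort 2 eye with data, including one that still holds its first optic.

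This matters because SAP 6 frames the comparison as non-inferiority. In a superiority test, untreated eyes in the test group usually make a positive finding harder to reach. In a non-inferiority test, eyes that never had the extra manipulation make the cohorts look more alike and so make non-inferiority easier to conclude. The Per Protocol set does not help: it is not used for ECC, and keeping the optic is foreseen by the protocol, so it is not evidently a major deviation.

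The lists of surgical details in Protocol 3.3.2 and 3.3.3 contain no explicit item for exchange attempted or completed. Unless this is captured elsewhere, the affected eyes could not be identified reliably afterwards.

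**Working it through.** **Can an unexchanged eye enter the comparison?**
1. The eye is assigned to Cohort 2 by astigmatism (Protocol 3.1).
2. A lens is implanted, the optic cannot be exchanged, and the first optic is kept (Protocol 3.3.2).
3. The eye meets the Implanted-Eye definition, which asks only for a successful implantation (Protocol 8.2.2, SAP 7.1.2).
4. If the fellow eye is implanted and both have 3-month ECC, the pair qualifies. No visible condition removes it.

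**Inputs from SAP 6.** Test used for sizing: "Based on a one-sided two-sample non-inferiority t-test with a significance level of 0.05". Evaluable pairs: 25, giving 25 eyes per cohort. Power: 80%. Assumed true difference: 5 percentage points. SD: 12.6. SAP 9 changes the test to paired: "the use of a paired t-test instead of a two-sample t-test to test the primary hypothesis".

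**Plan's own figures.** Enrolment reproduces: 25 / (1 − 0.20) = 31.25, rounded up to 32. The 80% power cannot be reproduced because no margin is visible. With 25 per cohort and SD 12.6, a two-sample t-test has 80% power when the margin lies 9.0 points from the true difference.

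**Size of the dilution.** Assume k of the 25 Cohort 2 eyes are unexchanged and carry no extra loss. The documents give no value for k. Observed difference = true difference × (25 − k)/25. With a true difference of 5:
- k = 1: 5 × 24/25 = 4.8
- k = 3: 5 × 22/25 = 4.4
- k = 5: 5 × 20/25 = 4.0

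The shift is 0.2, 0.6 or 1.0 points. The two-sample standard error is 12.6 × √(2/25) = 3.6. For the paired test with an assumed within-subject correlation of 0.5, the SD of the difference is 12.6 × √(2 × 0.5) = 12.6 and the standard error is 12.6/√25 = 2.5.

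**Effect on the error rate, for assumed margins.** Let the true exchange effect equal the margin M, so that non-inferiority should be declared 5% of the time. Dilution moves the mean k/25 × M inside the margin. From the noncentral t, with SD held at 12.6:

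| Assumed M | Test | k = 1 | k = 3 | k = 5 |
|---|---|---|---|---|
| 5 | two-sample | 5.6% | 7.0% | 8.6% |
| 5 | paired, correlation 0.5 | 5.8% | 7.9% | 10.4% |
| 10 | two-sample | 6.2% | 9.5% | 13.8% |
| 10 | paired, correlation 0.5 | 6.8% | 11.9% | 19.1% |

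These rates hold only if every unexchanged eye had no exchange manipulation. They are not estimates for this trial.

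**Cost of restricting to completed exchanges.** Take the stated 80% at 25 pairs as given (two-sample t, distance 9.0). Losing 1, 3 or 5 pairs leaves 24, 22 or 20, and power of 78.5%, 75.3% or 71.6%.

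**The case against.** **Redaction.** Protocol 8.3.1.2 on ECC is partly blacked out, as is the synopsis text on planned analyses. SAP 9 refers to a primary hypothesis and to a protocol definition of ECL that the visible text does not contain. A reader might infer that the plan has no completed-exchange or sensitivity analysis. The documents do not support that; they show only that the visible comparison rule lacks an exchange condition. This stands.

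**Direction.** A reader might infer that every unexchanged eye dilutes the effect. An optic that cannot be exchanged includes one where the attempt failed, and such an eye may lose as many cells as an exchanged eye, or more. The bias could then be nil or run against non-inferiority. This stands, and the arithmetic above covers only eyes without manipulation.

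**Partial cover elsewhere.** Capsular or zonular rupture, bag instability and miosis that prevents visualization are intraoperative exclusions (Protocol 3.2.3), and eyes disqualified on those grounds leave the analyses (Protocol 8.2). Some eyes where exchange is infeasible may already be gone. A failed exchange may also be reported as a device deficiency (Protocol 6.1.4), and deficiencies are summarized by cohort. Neither route ensures that unexchanged eyes are identified in the ECC analysis.

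**Assigned cohort is a legitimate basis.** It is, for the effect of a planned exchange, and it keeps trauma from failed attempts in view. It should remain. It does not by itself answer the objective about loss after an exchange.

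**Gating.** It is tempting to require both sets to meet the margin. In a pilot or feasibility study of about 25 pairs that is a debatable trade-off: it costs power, and the completed-exchange set is itself selected on surgical success and may look favourable for that reason. It is not proposed here.

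**Conclusion.** The point holds in limited form. On the visible text of both documents, a Cohort 2 eye that kept its first optic can be analysed as an exchange eye, which does not match the stated objective. The bias is assured to favour non-inferiority only where no exchange manipulation took place.

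Its size rests on an exchange-failure rate that the documents do not give. On the assumed counts it is small for one eye in 25 and becomes material at about three to five. The error-rate figures rest further on assumed margins. A margin near 14 points could be back-solved by adding the stated 5-point difference to the 9.0-point distance, but the documents do not confirm that reading and nothing here depends on it.

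The finding does not make the cohort comparison invalid. It supports an inexpensive addition to the plan.

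**What to change.** 1. Keep the ECC comparison by assigned cohort as it stands.
2. In SAP 5.6 and 7.1.2, pre-specify a supportive ECC comparison limited to pairs in which the Cohort 2 exchange was completed. Report it beside the main comparison, with no requirement that both meet the margin. If the redacted text already contains such an analysis, refer to it from these sections.
3. Record for each Cohort 2 eye whether the exchange was completed, attempted and failed, or not attempted. Confirm that the eCRF has this item.
4. List the unexchanged eyes by these categories with their ECC change.

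Cost: one data item, one listing and one further run of the same test, with no change to surgery or patient care. The supportive set has less power (about 78%, 75% or 72% instead of 80% if 1, 3 or 5 pairs are lost). It is also selected on surgical success, which is why it accompanies the main comparison and does not replace it. No increase in enrolment is needed for a supportive analysis.
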